#### I. BACKGROUND AND PURPOSE OF THE STUDY

#### 1 Background

The SureCRIC usability study is a two-part, validation study of a device intended to assist users with identification of surface anatomical landmarks relevant to creation of a surgical airway. The study design is based on FDA guidance to-date. The first part of the study is a human study that will focus on evaluating SureCRIC's intended use of helping to identify anatomical landmarks for establishing an airway. The human study will include representative novice, pre-hospital end users and human patient volunteers. The second part of the study is a manikin study will focus on evaluating SureCRIC use as part of the cricothyrotomy procedure and will include representative end users.

Per FDA feedback, human testing will be performed to evaluate the successful identification of the cricothyroid membrane (CTM) using the SureCRIC device. FDA agreed that the study results could be extrapolated to the following users and use cases: (a) intended user population including those who are more highly-trained and experienced at performing cricothyrotomy; and (b) the tracheotomy procedure where the same anatomic landmarks are identified and the procedure is performed in less chaotic, in-hospital environments. Twenty-four (24) medics (participants) will identify the CTM's of six (6) total healthy human volunteer subjects (subjects) representing a range of anatomical variation (including 5th, 50th, and 95th percentiles of height for men and women). Half of the participants will perform SureCRIC-aided CTM identification. The other half will use a standard, freehand approach for CTM identification. CTM location will be verified by an expert clinician.

Per FDA feedback, manikin testing will be performed to evaluate for potential interference of the SureCRIC with representative cricothyrotomy kits and tools, and to assess SureCRIC usability with these kits and tools. FDA agreed that the study results could be extrapolated to the following users and use cases: (a) intended user population including those who are more highly trained and experienced at performing cricothyrotomy; and (b) the tracheotomy procedure where the same anatomic landmarks are identified and the procedure is performed in less chaotic, in-hospital environments. Fifteen representative pre-hospital (novice) users and two representative experienced users will complete the cricothyrotomy procedure using three different representative cricothyrotomy kits for a total of 51 manikin testing scenarios. The cricothyrotomy kits will allow the participant to perform the cricothyrotomy procedure on the manikin via (a) the direct percutaneous access approach, (b) the Seldinger approach, and (c) the direct scalpel incision approach.

Participants in the study will complete study sessions that will consist of: 1) signing of necessary documents and pre-evaluation interview; 2) SureCRIC training (SureCRIC group only); 3) decay period (SureCRIC group only); 4) testing; 5) semi-structured interviews and critical error debriefing; 6) completion of knowledge tasks and labeling validation (SureCRIC group only); and 7) compensation arrangement.

## 2 Purpose of the Study

Overall validation study objectives are:

- To measure SureCRIC effectiveness with regard to the intended use of helping to identify anatomical landmarks
- To demonstrate that SureCRIC can be used by representative users under simulated conditions with minimal critical errors
- To evaluate the effectiveness of user training and instructional materials

The human validation study is one of two parts of the final evaluation method intended to demonstrate the safety and effectiveness of the device, labeling and related materials (e.g., materials, packaging, labeling). From the human factors perspective, the validation study serves to ensure that risks associated with the use of a medical device have been identified and adequately addressed, and that the impacts of residual risks are minimized. InnoVital Systems, Inc. (InnoVital) has engaged the National Center for Human Factors in Healthcare (Human Factors Center) to conduct the validation (also referred to as summative) study for the SureCRIC. Validation conducted by the Human Factors Center will focus on evaluating the use of the device by its intended users in simulated use environments. Specifically, the objectives of the human evaluation are:

- Primary endpoint: pass/fail assessment for CTM identification. The use of ultrasound to predefine / pre-mark CTM boundaries on the skin was discussed in the pre-submission supplement meetings. However, internal testing suggests that skin movements with SureCRIC use, and small head and neck movements by subjects may cause the pre-marked skin to shift and result in inaccurate assessments. This finding is in line with the limitations reported in a recent study evaluating CTM identification success in conscious human volunteers [Lamb 2015]. For the purposes of the current study, and as discussed with FDA, an expert in neck / airway anatomy (e.g., otolaryngologist or trauma surgeon) will palpate the area to verify accurate CTM localization.
- Secondary endpoints: time to CTM identification will be measured for descriptive statistics only per FDA request. Additionally, medics will be asked to report their confidence in accurate CTM identification (e.g., on a visual analog scale). Preparticipation, post-training, and post-participation human factors data will also be collected, as well as data from labeling validation.

The manikin validation study is one of two parts of the final evaluation method intended to demonstrate the safety and effectiveness of the device, labeling and related materials (e.g., materials, packaging, labeling). From the human factors perspective, the validation study serves to ensure that risks associated with the use of a medical device have been identified and adequately addressed, and that the impacts of residual risks are minimized. InnoVital Systems, Inc. (InnoVital) has engaged the National Center for Human Factors in Healthcare (Human Factors Center) to conduct the validation (also referred to as summative) study for the SureCRIC. Validation conducted by the Human Factors Center will focus on evaluating the use of the device by its intended users in simulated use environments. Specifically, the objectives of the manikin evaluation are:

• Primary endpoint: user-reported interference of the SureCRIC with the tools used for cricothyrotomy. Interference will be defined as problems with or errors caused by the SureCRIC with the use of these cricothyrotomy tools. Assessment for interference will

- be limited to the tools used up to and including the step where the SureCRIC is removed because after this step interference is no longer a concern.
- Secondary endpoints: NCHFH staff will assess the usability of the SureCRIC with the representative kits and tools and document possible procedure interference due to the SureCRIC. NCHFH staff will ask participants about these issues after completion of study participation.

The methods outlined in the protocol were determined based on feedback from the FDA obtained by InnoVital.

## II. CHARACTERISTICS OF THE RESEARCH POPULATION

### 1 Study Sites and Number of Subjects.

Both parts of the SureCRIC validation study will take place in the Human Factors Center's usability lab in downtown Washington, DC. The human portion of the study will consist of 24 novice (pre-hospital) participants and 6 volunteer patients as subjects. One back-up subject for each size will also be recruited to serve "on call" in case of a no-show in one of the primary subject roles. The manikin portion of the study will consist of 18 novice (pre-hospital) participants and 3 expert participants, for a total of 21 participants.

Pre-hospital (novice) study participants will be paramedics and/or combat medics (together referred to here as "medics"). Medics are non-expert users who are seldom called upon to perform cricothyrotomy. As such, medics represent the most challenging users. Medic recruitment will exclude participants with atypical knowledge of, training in, or experience with cricothyrotomy. For example, instructors of cricothyrotomy and airway management will be excluded. FDA agreed that novice users represent the most challenging users and that results obtained with novice users can be extrapolated to the rest of the intended user population which includes more highly trained and experienced users. All attempts will be made to ensure that 10% or more of the subjects recruited are left-handed, corresponding to the prevalence of left-handedness in the general population. For the human study, participants will be randomly pre-drawn into either an Experimental Group (using the SureCRIC) or a Control Group (not using the SureCRIC).

No participants in the study will have taken part in any formative activities or have previous familiarization with the SureCRIC. Participants will be recruited from the Washington, DC, or Baltimore area, and demographic information will be collected. User requirements will be screened by over-the-phone interviews and then validated during the informed consent process prior to the study.

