#### III. METHODS AND PROCEDURES

## 1 Methods and Data Analysis (Human Study)

The study will be a two-arm, open-label study. The Control Group will perform CTM identification with the standard, freehand approach. The Experimental Group will perform CTM identification with the help of the SureCRIC. The Experimental Group will be trained on

SureCRIC operation prior to testing. The expert verifier will not be blinded in order to reduce any error that may be introduced by SureCRIC removal and subsequent skin movement. Participants in the human study will complete study sessions that will consist of the following:

- 1. Signing of Documents and Pre-Evaluation Interview (~5 minutes). Prior to study participation, relevant information on clinical experience will be collected from all participants. Sample data points include handedness, years of and nature of clinical experience, cricothyrotomy training, and previous cricothyrotomy performance. Upon arrival, participants and subjects will be asked to sign an informed consent form that describes their role in the evaluation, explains risks involved, and consents to the use of audio and video recordings for analysis purposes. Participants and subjects will also be asked not to disclose any information about the product or materials they see during the training and evaluation.
- 2. Device Training (approximately 30 minutes Experimental Group only). Participants assigned to the Experimental Group will undergo SureCRIC training by [name]. SureCRIC training will consist of a review of the Instructions for Use (IFU) and supervised practice on a manikin and the trainer following a brief introduction to the device and operation. A copy of the IFU is attached. Participants assigned to the Control Group will not undergo SureCRIC training. Audio and video recording will be utilized for reference and use in data reduction and analysis (if applicable). Cameras will be positioned on tripods so as not to interfere with the training.

After completion of the training, the Human Factors Center will individually interview each participant using open-ended questions to garner subjective feedback on the training and instructional materials, as well as preparedness to perform SureCRIC-aided procedures.

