# 2 Methods and Data Analysis (Manikin Study)

The study will be a single-arm, open label study. Each of the participants will perform three cricothyrotomy procedures on a manikin. Each procedure will be performed with the SureCRIC and one of three representative cricothyrotomy kits. Participants in the manikin study will complete study sessions that will consist of the following:

- 1. Signing of Documents and Pre-Evaluation Interview (~5 minutes). Prior to study participation, relevant information on clinical experience will be collected from all participants. Sample data points include handedness, years of and nature of clinical experience, cricothyrotomy training with various approaches and kits, and previous cricothyrotomy performance. Upon arrival, participants will be asked to sign an informed consent form that describes participant's role in the evaluation, explains risks involved and consents to the use of audio and video recordings for analysis purposes. Participants will also be asked not to disclose any information about the product or materials they see during the training and evaluation.
- 2. Device Training (approximately 60 minutes). Participants will be introduced to each of the three cricothyrotomy kits as well as the SureCRIC and allowed to practice use on a manikin. SureCRIC training will consist of a review of the Instructions for Use (IFU) and supervised practice following a brief introduction to the device and procedure. A copy of the IFU is attached. Training with the three cricothyrotomy kits will include a review of the kit components and the IFU, and an opportunity to practice kit use, including with the SureCRIC, on a manikin model. Training will be conducted by [name]. Audio and video recording will be utilized for reference and use in data reduction and analysis (if applicable). Cameras will be positioned on tripods so as not to interfere with the training.

After completion of the training, the Human Factors Center will individually interview each participant using open-ended questions to garner subjective feedback on the training and instructional materials, as well as preparedness to perform SureCRIC-aided procedures.

3. Decay Period (minimum 60 minutes). After training, participants will be removed from the facility for a minimum of 60 minutes. Participants will then report to the testing facility at an agreed-upon time.

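### In the human study, the left-handed target covers both arms together and no stratified draw is described, so the Experimental Group could contain no left-handed medic.

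*Combined protocol and SAP*

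**What the plan says.** Section II.1 (Study Sites and Number of Subjects) states, in the paragraph on recruiting medics: "All attempts will be made to ensure that 10% or more of the subjects recruited are left-handed". The reason given is that this matches how common left-handedness is in the general population.

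The same paragraph then turns to allocation: "participants will be randomly pre-drawn into either an Experimental Group (using the SureCRIC) or a Control Group (not using the SureCRIC". Nothing in the protocol mentions stratification, blocking, or a minimum number of left-handers by arm or by study part.

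The sizes and roles come from section I.1 (Background): "Twenty-four (24) medics (participants) will identify the CTM's of six (6) total healthy human volunteer subjects (subjects". The split is even: "Half of the participants will perform SureCRIC-aided CTM identification". Section II.1 repeats the totals: "24 novice (pre-hospital) participants and 6 volunteer patients as subjects".

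Handedness is to be collected from participants before they take part. Section III.1 (Human Study) says: "Sample data points include handedness, years of and nature of clinical experience, cricothyrotomy training, and previous cricothyrotomy performance". It does not say whether this happens before the draw.

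The manikin study has a single arm. Section III.2 says: "Each procedure will be performed with the SureCRIC and one of three representative cricothyrotomy kits".

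**The concern.** Handedness matters for the person operating the device, not for the volunteer whose neck is examined. In the human study only the 12 Experimental medics operate it. A target that counts left-handers over all 24 medics can be met in full while every one of them is in the Control Group.

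What is at stake is coverage. One of the overall objectives in section I.2 is to show that representative users can use the SureCRIC, and the protocol itself names handedness as a feature that recruitment should represent. Pass/fail identification of the cricothyroid membrane is the primary endpoint of the human study and is not an endpoint of the manikin study. If no left-hander is drawn to the Experimental Group, the report can offer no observation of a left-handed user on that endpoint.

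The wording adds a small problem. The Background uses *subjects* for the six volunteers and *participants* for the medics, so the target sentence taken literally names the wrong people.

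**Working it through.** The plan gives no probability or calculated sample size on this point, so there is no figure to reproduce.

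**Inputs**
- Medics in the human study: 24 (sections I.1 and II.1).
- Experimental Group: half of 24 = 12 (section I.1).
- Target: 10% or more (section II.1). 0.10 × 24 = 2.4, so 3 left-handers just meet it.
- Draw: random. I assume a simple draw of 12 from 24, because no stratification is described.

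**Chance of no left-handed medic in the Experimental Group**

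With L left-handers among the 24, all 12 Experimental medics must come from the 24 − L right-handers:

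P = C(24 − L, 12) / C(24, 12)

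This is the same as requiring all L left-handers to fall in Control:

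- L = 2 (target narrowly missed): (12 × 11) / (24 × 23) = 132 / 552 = 23.9%
- L = 3 (target just met): (12 × 11 × 10) / (24 × 23 × 22) = 1,320 / 12,144 = 10.9%
- L = 4: (12 × 11 × 10 × 9) / (24 × 23 × 22 × 21) = 11,880 / 255,024 = 4.7%
- L = 5: C(19, 12) / C(24, 12) = 1.9%

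If each medic were instead assigned by an independent coin toss, L = 3 would give 0.5³ = 12.5%, so the result depends little on which simple method is used.

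**Chance of no left-handed SureCRIC user in either part**

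Take L = 3 in the human study and let manikin participants be left-handed by chance at the protocol's 10%. The protocol gives the manikin size in two ways: 15 novices plus 2 experienced users in section I.1, and 18 novices plus 3 experts in section II.1. I therefore show a range:

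- 15 manikin users counted: 0.1087 × 0.9¹⁵ = 2.2%
- 18 counted: 0.1087 × 0.9¹⁸ = 1.6%
- 21 counted: 0.1087 × 0.9²¹ = 1.2%

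If the target is instead met over both parts together, with 24 + 21 = 45 participants and 5 left-handers falling at random, the chance that all 5 are Control medics is C(12, 5) / C(45, 5) = 0.06%.

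**After stratifying by handedness**

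Three left-handers split 2:1 or 1:2, and the 21 right-handers split 10:11 or 11:10 to keep the arms at 12 each. The chance of none in the Experimental Group falls from 10.9% to 0. Two left-handers split 1:1, so 23.9% also falls to 0. With a single left-hander it stays at 50% whichever way the draw is done.

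**The case against.** There is a good case that this is minor, and most of it stands.

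- **The manikin study supplies left-handed users.** It has one arm and every procedure uses the SureCRIC. A reader might infer that the whole validation could end with no left-handed user. The documents do not support that: the chance is about 0.06% to 2.2%. The manikin study cannot fill the gap on the human endpoint, however, because its own primary endpoint is interference with the cricothyrotomy tools.
- ***Subjects* is a slip.** A reader might infer that the target binds only the six volunteers and leaves the medics with none, which at 10% prevalence would give 0.9¹² = 28.2%. The sentence stands among the medic recruitment rules, handedness is recorded from participants in both parts, and the headings of sections II.1 and II.2 use *Subjects* loosely for participants. Medics are evidently meant.
- **No comparison can be biased.** A reader might infer that chance imbalance in handedness distorts the contrast between arms. The human study data analysis text rules out comparisons and promises descriptive data only, and nothing in the documents says that handedness affects identification. This objection stands in full.
- **Left-handed performance is not a stated aim.** The target is justified by population prevalence, and no endpoint concerns left-handers. So the plan does not fail an aim of its own. The link is only to the general objective of use by representative users.
- **A simple draw is inferred from silence.** The sponsor may already intend to balance handedness. If so, the text needs only to say it.
- **The odds favour coverage.** With 3 left-handers, at least one is in the Experimental Group 89.1% of the time (100% − 10.9%), and 10% is a floor.

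**Conclusion.** The point holds as a coverage gap limited to the human study. As written, the target can be met while no left-handed medic uses the SureCRIC on a human neck. The chance is 10.9% with 3 left-handers among 24, and runs from 23.9% with 2 to 4.7% with 4. The lower count is relevant because the target is best-effort only.

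This rests on three assumptions: the target is meant for the medics, it is applied to the 24 in the human study, and the draw is simple.

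The gap does not extend to the study as a whole, and it does not threaten the validity of any planned analysis. One or two left-handed users would in any case show that such users were observed, not estimate how well they perform. The point is a low-priority improvement, worth making because it costs almost nothing.

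**What to change.** 1. In section II.1, replace *subjects* with *participants* in the left-handedness sentence.
2. Ask about handedness at the phone screen that section II.1 already provides for, so that it is known before the draw.
3. State that the human-study pre-draw is stratified by handedness, with left-handers divided between the arms as evenly as possible and 12 medics kept in each arm.
4. Add handedness to the raw data listing. The example table shows participant, group, success, confidence score and time, but not handedness.

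A separate left-handed minimum in each arm is not needed. Applying 10% to 12 medics would round up to 2, which is 16.7% and above the protocol's own target, while stratification alone already guarantees at least one left-handed Experimental medic whenever two or more are recruited.

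The cost is one extra screening question, a two-stratum draw list and one column in a table. No additional participants are required. The only constraint is that handedness must be recorded before allocation.

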## 2 Gender, Age, Racial or Ethnic origin of Subjects.

No specific characteristics (e.g. gender, age, racial or ethnicity origin) are required or will be taken into consideration for recruitment of the participants. The study population will be limited to the characteristics of the available participants.

#### 3 Inclusion Criteria.

Pre-hospital study participants will be registered and licensed paramedics (https://www.nremt.org/rwd/public/document/paramedic) and/or current or former combat medics (e.g., http://www.cs.amedd.army.mil/ems.aspx). In the pre-submission meeting, FDA agreed that civilian paramedics and military medics may be considered part of a single user group because many of them have similar training and often switch between the two clinical fields. As novice users, they represent the most challenging population.

The patient volunteers (subjects) in the human study will be healthy male and female volunteers who meet the height percentiles discussed with FDA. Six subjects representing the 5th, 50th, and 95th percentile heights for males and females will be included:

- Subject 1: 4'9" female, up to 138 lb (5th percentile female)
- Subject 2: 5'3" female, up to 169 lb (50th percentile female)
- Subject 3: 5'9" female, up to 202 lb (95th percentile female)
- Subject 4: 5'2.5" male, up to 166 lb (5th percentile male)
- Subject 5: 5'8.5" male, up to 199 lb (50th percentile male)
- Subject 6: 6'2.5" male, up to 236 lb (95th percentile male)

Per FDA request, three experienced users will be included in the manikin study to provide additional insight that may otherwise be overlooked by the novice users, as discussed in the pre-submission supplement meeting. These users will be medics, physician assistants, physicians, or surgeons who are / have:

- An instructor of cricothyrotomy, airway management, or neck anatomy OR
- Experience performing cricothyrotomy on a patient in the last 6 months OR
- A trauma surgeon, interventional pulmonologist, or otolaryngologist

An expert clinician (site verifier) will be recruited to assess whether the sites identified on subjects by users is the CTM. The expert will fit any one of the following inclusion criteria:

- Otolaryngologist
- Trauma surgeon
- Interventional pulmonologist
- Emergency physician who is / has been an instructor of cricothyrotomy

